**Treatment Period 1 and 2 (subjects without dose change):**

Follow-up or Study Completion Visit date and time (whichever occurs later) – date and time of first SC administration of study treatment + 1.

**Treatment Period 1 and 2 (subjects with dose change):**

Portion before dose change:

Date and time of dose change – date and time of first SC administration of study treatment + 1.

Portion after dose change:

Data will not be included in the summary tables.

Date and time of first SC administration of study treatment is Week 1 Day 6 or Week 1 Day 1 for those with [REDACTED] an IV loading dose, respectively.

### 8.3 Laboratory Parameters

A laboratory value that is outside the reference range is either high abnormal (value above the upper limit of the normal reference range) or low abnormal (value below the lower limit of the normal reference range). An abnormal laboratory value is not necessarily of potential clinical interest.

For laboratory safety parameters, any instances of absolute values being outside the reference range or changes at any visit after study start that are considered by the investigator as clinically significant must be recorded in the eCRF as AEs. In addition, at the investigator's discretion, any changes or trends over time in laboratory parameters can be recorded in the eCRF as AEs if such changes or trends are clinically relevant, even if the absolute values are within the reference range.

## 9 Study Population

### 9.1 Disposition of Subjects

Subject disposition will be summarized using all subjects who provided informed consent.

The following will be presented in summary tables by treatment as specified in Section 7. The results will be presented over all subjects and for subjects with C1-INH and FXII/PLG HAE. Percentages will be based on the Screening population:

- Number of subjects who provided informed consent;
- Number and percentage of subjects who underwent Screening;
- Number and percentage of subjects who entered the Run-in Period;
- Number and percentage of subjects still in the Run-in Period (only for interim analysis);
- Number and percentage of subjects who were not assigned to study treatment;
- Number and percentage of subjects who were assigned to study treatment in Treatment Period 1;
- Number and percentage of subjects who were assigned to study treatment in Treatment Period 2;
- Number and percentage of subjects still in Treatment Period 1 (only for interim analysis);

- Number and percentage of subjects still in Treatment Period 2 (only for interim analysis);
- Number and percentage of subjects who have a planned dose reduction from █ mg to █ mg in Treatment Period 2 (following Amendment 2);
- Number and percentage of subjects who completed Treatment Period 1;
- Number and percentage of subjects who completed Treatment Period 2;
- Number and percentage of subjects still in the study (only for interim analysis);
- Number and percentage of subjects who completed the study;
- Number and percentage of subjects who discontinued the study in the Run-in Period with reason for discontinuation (percentages based on the number who discontinued);
- Number and percentage of subjects who discontinued the study in Treatment Period 1 with reason for discontinuation (percentages based on the number who discontinued);
- Number and percentage of subjects who discontinued the study in Treatment Period 2 with reason for discontinuation (percentages based on the number who discontinued);
- Number and percentage of subjects who discontinued the study in any period with reason for discontinuation (percentages based on the number who discontinued).

A by-subject listing for all available data with the information as described in Section 7 and in addition screening status (failed or qualified), reason for screening failure (in- or exclusion criterion numbers), date and time of informed consent, date of eligibility for Run-in, reasons for non-eligibility for Run-in, date of eligibility for Treatment Period 1, date and time of randomization, reason for non-eligibility for randomization, date and time of first IV, first SC, and last treatment, date of study completion or discontinuation, and reason for study discontinuation will be presented. Another listing for all available data will present the individual visit dates for all visits (scheduled and unscheduled) which the subject attended.

## 9.2 Protocol Violations

Protocol violations are those protocol deviations which may identify subjects who should be excluded from one or more analysis population(s). Listings showing subjects with protocol deviations will be generated prior to each interim and the final analysis to identify subjects who may have these protocol violations. During the Data Review Meetings, the subject assignment to analysis populations will be discussed in detail based on the consolidated protocol deviations from the █ along with the listings of the potential protocol violations specified below. It cannot be ruled out that during the discussion of protocol deviations, additional violations which are not listed below will be considered to

have a significant impact and will thus lead to exclusion of subjects from analysis population(s). The decisions made during the Data Review Meetings will be documented in detail in the Data Review Meeting minutes and may modify the specifications in the list below. The Data Review Meeting minutes will be agreed upon prior to each interim and final analysis.

Potential Protocol Violations	Potential Exclusion From Analysis Population
Subject did not provide informed consent (informed consent date missing)	Screening, Safety, ITT, PP, PK, (b) (4)
Subject randomized but not treated with study treatment	Safety, PP, PK, (b) (4)
Subjects treated with incorrect study treatment	PP, potentially PK, (b) (4)
Subject randomized and treated but does not have at least one measurable PK concentration	PK
Subject randomized and treated but does not have at least one (b) (4) measurement	(b) (4)
Subject randomized and treated but without primary efficacy assessment	PP
Subject randomized and treated but violated inclusion or exclusion criteria	PP, potentially also PK, (b) (4)
Subject randomized and treated but compliance outside 80-120%	PP, potentially also PK, (b) (4)
Subject randomized and treated but received prohibited concomitant medication	PP, potentially also PK, (b) (4)

Protocol deviations caused by the Corona Virus Disease 2019 (COVID-19) pandemic will be documented throughout the entire study. They will be assigned as a separate protocol deviation category “COVID-19”, will be listed, and discussed during the Data Review Meetings. They will be summarized separately from the other protocol deviations and will also be discussed in the CSR.

Prior to each Data Review Meeting, a list of concomitant medications used in the study will be provided to CSL as an Excel file in the same format as the corresponding listing of concomitant medications in the TFL shells. This Excel file will be reviewed by CSL and

concomitant medication potentially interfering with the PK/**col** analysis or with the efficacy analysis will be flagged.

A summary table with the number and percentages of subjects with

- Inclusion and exclusion protocol violations;
  - All significant protocol violations including inclusion and exclusion violations
- will be provided. Number and percentage of subjects in the Screening, Safety, ITT, PP, PK, and **col** population will be provided.

The following by-subject listings for all available data with the information as described in Section 7 and in addition information as listed below will be provided:

- Randomized and actual treatment;
- All inclusion and exclusion protocol deviations;
- All other protocol deviations with an indication whether this is a significant violation or minor deviation and from which analysis population the subject will be excluded;
- COVID-19 protocol deviations.

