## 6.2 Intent-to-Treat Population

The Intent-to-Treat (ITT) population will consist of all subjects who provide informed consent, undergo any study screening procedure, and who are assigned to treatment in Treatment Period 1 or to treatment in Treatment Period 2, regardless of whether they receive the investigational product. The ITT population will be analyzed using the treatment to which the subject was assigned in Treatment Period 1, in Treatment Period 2 at Week 13, or [REDACTED] mg after dose reduction from [REDACTED] mg following Amendment 2 in Treatment Period 2 (only applicable for C1-INH HAE subjects), regardless of the actual treatment received.

Technical Note: Subjects who belong to the Screening population and have randomization date available for Treatment Period 1 or Treatment Period 2 will be included for the corresponding Treatment Periods. Thus, the ITT will be assigned within treatment period.

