## 6.4 Per-Protocol Population

The per-protocol (PP) population will consist of all subjects in the ITT population, excluding subjects who have a significant protocol violation. Protocol violations which will lead to exclusion from the PP population will be reviewed and agreed prior to conducting each of the interim analyses and before database lock.

Technical Note: Subjects who belong to the ITT population and who do not have significant protocol violations which lead to exclusion from PP as decided during the Data Review Meeting will be included.

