## 10.4 Treatment Compliance

Compliance will be summarized for the ITT population for the SC injections in each treatment period and both periods together for subjects who received the same dose continuously during both treatment periods (data will only be included until the date of the planned dose reduction following Amendment 2 in Treatment Period 2). The IV infusions will not be included in the compliance analysis. The administered volume of each injection will be taken from the data base. The study medication has a concentration of CCI mg per mL. To maintain the blind, the doses in the blinded part of Treatment Period 1 will be volume-normalized. It is planned that all SC injections will contain mL. If in the blinded study part, the subject is randomized to CCI mg CSL312, the mL injection will contain purely the study medication. For the CCI mg and the CCI mg CSL312 group, the study

medication will be diluted in a [REDACTED] and [REDACTED] ratio, respectively. For the derivation of the actual dose, it is assumed that the dilution will take place as planned. For the open-label part, the study medication is not diluted.

From the actual volume of an injection as in the database and considering the randomized dose, the actual dose will be derived as:

$$\text{Actual dose (mg)} = (\text{actual volume [mL]} / K [\text{mL/mg}]) * 100,$$

where  $K =$  [REDACTED] or [REDACTED] mL/mg for [REDACTED] mg, [REDACTED] mg, or [REDACTED] mg CSL312 q4wk in the blinded arm and [REDACTED] for the open-label arms.

Compliance for dose (mg) will be calculated as

$$\text{Compliance (\%)} = [\text{total cumulative actual dose} / \text{total planned dose}] * 100,$$

where the total planned dose will be derived from the subject's exposure and planned treatment schedule (q2wk or q4wk) as

$$(\text{duration of exposure in days} / (7 * X)) * \text{planned dose} + \text{planned dose}$$

where (duration of exposure in days) is rounded down to the nearest integer which can be divided by 7 and  $X = 2$  or  $4$  corresponds to q2wk or q4wk, respectively.

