Only the administered doses will be considered for the total cumulative actual dose which are identical to the planned treatment. The planned treatment is the randomized treatment in Treatment Period 1 and in Treatment Period 2 prior to the planned dose reduction following Amendment 2. For C1-INH HAE subjects randomized to [REDACTED] mg CSL312 in Treatment Period 2, the planned treatment after dose reduction changes to [REDACTED] mg CSL312. Exposure duration will depend on the treatment period and subject's course of the study. Definitions are provided in Section 8.2.8.

The following summaries will be provided:

- Descriptive statistics for compliance (%) over the entire treatment period, for Treatment Period 1 plus the first three doses of Treatment Period 2 (administration on site), and for Treatment Period 2 after the first three doses (administration at home);
- Number and percentage of subjects in the compliance categories < 80%, 80 – 120%, and > 120% and < 90%, 90 - 110%, and > 110% for the periods specified above.

A by-subject listing as specified in Section 7 and with the following additional information will be provided:

- Randomized, planned and actual treatments;

- Compliance in Treatment Period 1 plus the first three doses of Treatment Period 2, after the first three doses in Treatment Period 2, and over the entire study.

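### Per-protocol membership is not tied to Treatment Period 1, and no compliance value planned in the SAP correctly measures adherence in that period

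*SAP*

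**What the plan says.** - **Endpoint and populations.** SAP 10.1 and protocol 10.3.2.1.1 confine the primary endpoint to the TP1 efficacy period, from the first SC dose (Day 6) to Week 13. ITT is the primary analysis and PP the secondary one.
- **PP definition.** SAP 6.4: "The per-protocol (PP) population will consist of all subjects in the ITT population, excluding subjects who have a significant protocol violation". No period is named, nor is one in protocol 10.2.3. Exclusions are settled before each interim analysis and before database lock.
- **ITT, by contrast.** The technical note in SAP 6.2 ends: "Thus, the ITT will be assigned within treatment period".
- **Exclusion criteria.** The SAP 9.2 table links "Subject randomized and treated but compliance outside 80-120" (per cent) to exclusion from PP, and has a similar row for prohibited medication. Neither row names a period. The table is headed as potential violations and potential exclusions.
- **Compliance values.** SAP 10.4 opens with "Compliance will be summarized for the ITT population for the SC injections in each treatment period". Its by-subject listing, however, gives two values as "Compliance in Treatment Period 1 plus the first three doses of Treatment Period 2, after the first three doses in Treatment Period 2". The third value it lists covers the whole study. Nothing says which value feeds the 9.2 row.
- **Compliance formula.** SAP 10.4 divides the dose received by a planned dose derived from exposure. The planned number of doses is exposure days divided by 7X, plus one, with X = 4 for q4wk. Exposure "is rounded down to the nearest integer which can be divided by 7" and is taken from SAP 8.2.8.

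**The concern.** A PP analysis of a TP1 endpoint should show the effect in subjects treated as planned during TP1. If the criterion is applied to values that mix periods, adherence after the endpoint window has closed can decide who is in that analysis, and a missed TP1 dose can be diluted by later doses. Because PP is reviewed again before each interim and before database lock, the TP1 PP set can also change after TP1 is complete. Each blinded arm has 8 subjects, so one or two wrong classifications are a visible share of an arm.

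**Working it through.** The documents state no compliance figure to reproduce, so the check applies the criterion to the nominal q4wk schedule.

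**Inputs**
- TP1 SC doses: Days 6, 35 and 63, so 3 (protocol, q4wk schedule footnotes).
- TP2 SC doses without extension: Days 91, 119 and 147, then every 28 days to Day 371, so (371 − 91)/28 + 1 = 11 (protocol 3.2.2). Whole study: 14.
- Exposure (SAP 8.2.8):
  - TP1, entering TP2: 91 − 1 − 1 + 1 = 90 days.
  - TP1, not entering TP2: 91 − 1 + 1 = 91 days.
  - Both periods: 399 − 1 + 1 = 399 days.
- Acceptable range: 80–120% (SAP 9.2).

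**Planned doses by the SAP 10.4 formula**
- TP1, entering TP2: 90 rounds down to 84; 84/28 + 1 = 4.
- TP1 only: 91/28 + 1 = 4.25.
- Whole study: 399/28 + 1 = 15.25.

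**Case A: one TP1 dose missed, all others taken**

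| Value | By scheduled doses | By SAP formula |
|---|---|---|
| TP1 alone | 2/3 = 66.7% | 2/4 = 50% |
| TP1 + first three TP2 doses | 5/6 = 83.3% | 5/6.25 = 80.0% or 5/7 = 71.4% |
| Whole study | 13/14 = 92.9% | 13/15.25 = 85.2% |

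The two SAP results in the middle row arise because the SAP does not define where this exposure ends. Ending at Day 147 gives 147/28 + 1 = 6.25 planned doses. Running to Day 174 gives 168/28 + 1 = 7. On the whole-study value the subject is inside the range either way.

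**Case B: all three TP1 doses taken, doses missed only in TP2**
- Whole study, two missed: 12/14 = 85.7% by scheduled doses (inside), but 12/15.25 = 78.7% by the SAP formula (outside).
- Whole study, three missed: 11/14 = 78.6% by scheduled doses (outside).
- TP1 + three, two of those three TP2 doses missed: 4/6 = 66.7% by scheduled doses (outside).
- TP2 after the first three doses, two of eight missed: 6/8 = 75% by scheduled doses (outside).

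**Case C: the per-period summary, full TP1 adherence**
- Entering TP2: 3/4 = 75% (outside).
- Not entering TP2: 3/4.25 = 70.6% (outside).

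The overcount has two sources. Exposure runs to Week 13 and so already covers the interval after the third SC dose, yet one more dose is added. Exposure also starts at the IV loading dose on Day 1, although 10.4 leaves IV infusions out of compliance.

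**First interim.** With one TP1 dose missed, study-to-date compliance reaches 80% after 2 TP2 doses by scheduled doses (4/5). By the SAP formula it takes 3 doses if the cut-off falls on a dosing day (5/6.25) and 6 if it falls on the day before the next dose (8/10).

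**The case against.** The strongest reply is that the text allows a period-specific reading. PP is drawn from ITT, ITT is assigned within period, and 10.4 announces a compliance summary for each period. Concomitant medications carry period flags (SAP 9.4), so reviewers can see when a prohibited drug was taken. The 9.2 exclusions are only potential, and Data Review Meetings may amend the list and must document their decisions. The placebo comparisons are tested only at the first interim (SAP 4.6.1), when later-enrolled subjects have little or no TP2 data. ITT is primary throughout.

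Most of this stands as a limit on the effect. Misclassification is possible but not automatic. At the first interim, dilution affects mainly earlier-enrolled subjects. A reader might infer that TP1 compliance is never computed; that goes too far, because a per-period summary is announced. It does not rescue the criterion, however: by the 10.4 formula that summary puts a fully adherent q4wk subject below 80% (Case C). Having PP drawn from a period-specific ITT set does not say that violations are judged within period, and no text links the 9.2 row to a TP1 value. Meeting discretion leaves a rule that can be fixed in advance to case-by-case judgement, and at later reviews the TP1 results will already have been produced.

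**Conclusion.** The point holds for the secondary (PP) analysis of the primary endpoint. PP membership is not tied to the period analysed, and none of the planned compliance values classifies TP1 adherence correctly. For subjects who enter TP2 the listed values can keep someone at 67% in TP1 (93%, or 85% by the SAP formula, over the whole study). They can also flag someone at 100% in TP1 (79% by the SAP formula after two missed TP2 doses). The only TP1-specific value scores full adherence at 75% or 70.6%.

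These figures assume nominal visit days, full volume at each injection, the same dose in both periods, no Amendment 2 dose reduction and no TP2 extension.

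Two further inferences are tempting but unsupported. One is a stated loss of power: the documents do not say how many subjects would be excluded, and the PP analysis was not separately sized. The other is that the rule favours CSL312: placebo subjects may also enter TP2, on CSL312, and face the same rule, so the direction of any bias cannot be established. The ITT analysis is unaffected. The SAP should be corrected, but the primary conclusion is not at risk from this point.

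**What to change.** 1. In SAP 6.4 and 9.2, assign PP within treatment period, as 6.2 does for ITT.
2. For the TP1 PP set, count only violations that occur before the first TP2 dose, or before the Week 13 or Study Completion Visit for a subject who does not enter TP2.
3. Reword the 9.2 row as TP1 SC compliance outside 80–120%. Compute it as SC dose received divided by the SC dose scheduled up to the end of the subject's TP1 participation (3 doses for q4wk completers), replacing the exposure-based denominator. Restricting the present formula to TP1 would not be enough, since it would flag fully adherent q4wk completers.
4. Add this value to the by-subject listing and the category table in 10.4.
5. Use a separate TP2 PP flag for TP2 summaries.

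With these changes full TP1 adherence scores 3/3 = 100% and one missed dose 2/3 = 66.7%, whatever happens in TP2. The cost is SAP wording and one derived value; no new data are needed.

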### 9.3 Demographic and Baseline Characteristics

Demographic and baseline subject characteristics will be summarized for the ITT and PP populations.

BMI will be defined as body weight [kg]/height [m^2]

The following summaries will be provided:

- Demographic characteristics: sex, race, ethnicity, age, height and body weight at Screening, and BMI. As only adults will be included, no age groups will be formed.
- HAE history: HAE type (C1-INH Type I, C1-INH Type 2, FXII HAE, PLG HAE), number of HAE attacks before Screening for subjects without prophylactic HAE therapy (C1-INH HAE: over a consecutive 2-month period during the 3 months before Screening; FXII/PLG HAE: during the 3 months before Screening), number and percentage of subjects who took prophylactic HAE therapy, number of HAE attacks before the start of prophylactic therapy (C1-INH: over any consecutive 2-months period during 3 months before the start of prophylactic HAE therapy; FXII/PLG: during the 3 months before the start of prophylactic therapy).

- Medical history will be presented by SOC and PT – include medical history terms with end date / evidence for end date prior to informed consent date.
- Concomitant diseases will be presented by SOC and PT – include medical history terms with end date / evidence for end date after informed consent date or flagged “Ongoing” or end date missing.

Medical history and concomitant diseases will be coded by Medical Dictionary for Regulatory Activities (MedDRA). There will be periodic updates of the MedDRA version. The latest licensed version will be used, and version updates will be implemented upon availability.

By-subject listings for all available data with the information as described in Section 7 will be provided for:

- Demographic data (sex, age, race, ethnicity, height at Screening, body weight at Screening, and BMI);
- Disease characteristics (HAE type, number of HAE attacks before Screening, prophylactic HAE therapy [Yes, No], number of HAE attacks before the start of prophylactic HAE therapy);
- Medical history and concomitant diseases (medical history term, SOC, PT, start and end date or ongoing flag);
- Reproductive system findings (childbearing potential, method of birth control, date and time of pregnancy test, and pregnancy test result).

#### **9.4 Concomitant Medications**

Prior and concomitant medication will be summarized for the Safety population. On-demand HAE medication will be summarized as separate block within the summaries of prior and concomitant medication (as a “virtual” ATC class “On-demand HAE Medication”). The on-demand HAE medication will also be reported in their original ATC class. For the “Any Medication” entry, the virtual ATC class “On-demand HAE Medication” will be excluded to avoid counting the medication twice.

Concomitant medications will be coded using World Health Organization Drug Dictionary Enhanced (WHO-DDE) B3 version March 2018 or more recent. The summary of concomitant medications will show the number and percentage of subjects taking

concomitant medications by Anatomical Therapeutic Chemical (ATC) class and PT. ATC Level 4 will be used for the summary tables and listing unless coding is not available at level 4. In these cases, level 3 ATC name will be used. Similarly, if the level 3 ATC name is not available then the level 2 ATC name will be used and if the level 2 ATC name is not available then the level 1 ATC name will be used. These replacements will only be made for missing ATC level 4. ATC Level 1 information will be included in the dataset created but will not appear in the listing or summary except when all other levels are not available.

The following classification of concomitant medication related to start date of study treatment in each treatment period will be applied:

- Assign to 'Prior Only' if the concomitant medication start date and end date is prior to study treatment start date of the respective treatment period; if the subject has not taken any study treatment; or the concomitant medication start date is missing and the concomitant medication end date is before the study treatment start date of the respective treatment period;
- Assign to 'Prior and Concomitant' if the concomitant medication start date is prior to study treatment start date of the respective treatment period and the concomitant medication end date is on or after study treatment start date of the respective treatment period or ongoing treatment;
- Assign to 'Concomitant Only' if the concomitant medication start date is on or after the study treatment start date of the respective treatment period.

If medication start and/or stop dates are partially or completely missing, medications will be assumed to be 'Concomitant Only', unless there is clear evidence (through comparison of partial dates) to suggest that the medication started prior to the date of the first administration of study treatment of the respective treatment period. If there is clear evidence to suggest that the medication started prior to the date of first administration of study treatment of the respective treatment period (the available parts of the date are prior to the corresponding parts of the date of first administration of study treatment of the respective treatment period), the medication will be assumed to be 'Prior and Concomitant', unless there is clear evidence to suggest that the medication stopped prior to the date of the first administration of study treatment of the respective treatment period (the available parts of the medication end date are prior to the corresponding parts of the date of first administration of study treatment of the respective treatment period). If this is the case, the medication will be considered 'Prior Only'.

For medications which are considered ‘Prior and Concomitant’ or ‘Concomitant Only’ in Treatment Period 2 or in both treatment periods, the dose change needs to be considered. It should be noted that the medication flags will no longer be exclusive. The same medication may be “Concomitant Only” for Treatment Period 1 and for both treatment periods, but “Prior Only” for Treatment Period 2.

The following flags will be assigned:

CCI

CCI

In the summary of concomitant medications, each subject will be counted once within each PT (Any Medication, ATC Class, and PT). For example, if a subject takes Amoxicillin on two separate occasions, the subject will be counted only once under the medication “Amoxicillin”, once in the corresponding ATC class, and once for “Any Medication”. The number and percentages of subjects based on the Safety population along with the number of reports will be presented for ‘Prior’. For ‘Prior and Concomitant’ the number and percentage of subjects will be presented together with ‘Concomitant Only’ medications.

A by-subject listing for all available data with the information as described in Section 7 and in addition medication/treatment, start and end date or ongoing, dose, route, frequency, primary indication for the concomitant medication, AE identifier if applicable, medical history identifier if applicable, and concomitant medication flag (Prior Only [P1, P2], Prior and Concomitant [PC1, PC2, PC2\_after, PC12], Concomitant Only [C1, C2, C2\_after, C12]) will be provided.

